Protocol Summary

Study Compound: Atogepant

Phase: 3

Study Objective:

Safety and tolerability: To evaluate the safety and tolerability of treatment with atogepant 60 mg once daily over a 12-week duration for the prevention of migraine in Chinese participants who completed Study 3101-303-002 (chronic migraine [CM]).

Efficacy: To evaluate the efficacy of treatment with atogepant 60 mg once daily when administered over 12 weeks for the prevention of migraine in Chinese participants with CM.

Clinical Hypotheses:

Atogepant 60 mg once daily is safe and well tolerated when administered over 12 weeks for the prevention of migraine in Chinese participants with CM who completed lead-in study 3101-303-002.

Study Design

Structure: Multicenter, open-label, 12-week, safety extension study conducted in China.

Duration: The study will consist of a 12-week treatment period, followed by a 4-week safety follow-up period, for a total duration of 16 weeks.

Study Intervention: Atogepant 60 mg once daily

Control Intervention: Not applicable

Dosage/Dose Regimen: Atogepant 60 mg orally once daily will be administered for 12 weeks.

Randomization: Not applicable

Visit Schedule: After Visit 1, study visits will occur every 4 weeks during the 12-week treatment period. A safety follow-up visit will occur 4 weeks after the last dose of atogepant. For details, please see [Table 1](#), the Schedule of Visits and Procedures.

Study Population Characteristics

Number of Participants/Sites: All participants who complete Study 3101-303-002, and meet all eligibility requirements, may participate in this study.

Condition/Disease: Migraine with aura or migraine without aura (ICHD-3 Section 1.1 or Section 1.2; see [Section 12.1.1](#))

Key Inclusion Criteria:

- Eligible participants who completed the double-blind treatment period (Visit 7), and the safety follow-up period (Visit 8), if applicable, depending on the timing of study initiation, of Study 3101-303-002 without significant protocol deviations (eg, noncompliance to protocol-required procedures) and who did not experience an AE that, in the investigator's opinion, may indicate an unacceptable safety risk

Key Exclusion Criteria:

- Participants requiring any medication, diet, or nonpharmacological treatment on the list of prohibited concomitant medications or treatments (see Section 4.5.2 and [Attachment 12.2](#)), that cannot be discontinued or switched to an allowable alternative. Concomitant medications with demonstrated efficacy for the prevention of migraine is exclusionary, except that participants from lead-in study 3101-303-002 taking 1 medication with demonstrated efficacy for the prevention of migraine may participate in the current study provided that the dose was stable prior to the lead-in study and the participant is willing to continue taking that medication.
- Participants with an ECG indicating clinically significant abnormalities at Visit 1
- Participants with hypertension (sitting systolic BP > 160 mm Hg or sitting diastolic BP > 100 mm Hg) at Visit 1
- Participants with a significant risk of self-harm (C-SSRS), or of harm to others (investigator opinion); participants who report suicidal ideation with intent, with or without a plan, (ie, Type 4 or 5 on the C-SSRS) since the last visit, must be excluded
- Participants with clinically significant hematologic, endocrine, cardiovascular, pulmonary, renal, hepatic, gastrointestinal, or neurologic disease

Response Measures

Safety—AEs, physical examinations, clinical laboratory determinations, vital sign measurements, ECG parameters, and the C-SSRS

Efficacy—The efficacy of atogepant for the prevention of migraine will be assessed based on information recorded by the participant. An eDiary will be used daily at home to collect data on headache duration, headache characteristics, non-headache migraine symptoms, and acute medication use, which will be collectively applied to define migraine days, and headache days per the criteria listed in Sections [6.2.1](#), [6.2.2](#) and [6.2.3](#).

General Statistical Methods and Types of Analyses:

All safety analyses will be performed using the safety population, which consists of all participants who took at least 1 dose of study intervention (atogepant) in this extension study. All efficacy analyses will be performed using the mITT population, consisting of all participants who received at least 1 dose of study intervention (atogepant) and had at least 1 evaluable post-baseline 4-week period of eDiary data, in this extension study.

The safety parameters will include AEs, clinical laboratory evaluations, vital sign measurements, ECG parameters, and the C-SSRS. For each of the clinical laboratory, vital sign, and ECG parameters, the baseline value as defined for the lead-in study (3101-303-002) will be used as the baseline in this extension study. Continuous variables will be summarized by the number of participants and mean, SD, median, minimum, and maximum values. Categorical variables will be summarized by number and percentage of participants.

Efficacy endpoints include change from baseline in monthly migraine days, change from baseline in monthly headache days, at least a 50% reduction from baseline in monthly migraine days, and other endpoints. The baseline value as defined for the lead-in study (3101-303-002) will be used as the baseline in this extension study. For analysis purposes, 4 weeks (28 days) will be considered as 1 month. Descriptive statistics will be provided by visit for all efficacy endpoints based on the mITT population using the observed cases approach.

Sample Size Calculation:

Chinese participants who complete Study 3101-303-002, and meet all eligibility requirements, may participate in this extension study. Approximately 120 Chinese participants are expected to participate in this extension study.

[figure not shown]
Figure 1. Study Diagram

Table 1. Schedule of Visits and Procedures

Study Period	Open-label Treatment Period (12 weeks)				Safety Follow-up Period (4 weeks)
	Visit 1 ^a	Visit 2	Visit 3	Visit 4/ET	
Visit #	Day 1	Week 4 (Day 28)	Week 8 (Day 56)	Week 12 (Day 84)	Visit 5/EOS
Week (Day)					
Visit Windows	N/A	± 3 days	± 3 days	± 3 days	± 3 days
Obtain informed consent and participant privacy	X				
Access IWRS	X	X	X	X	X
Assess inclusion/exclusion criteria	X				
Collect medical history ^b	X				
Perform physical examination	X				X
Collect vital sign measurements ^c	X	X	X	X	X
Perform ECG	X		X	X	
Perform urine pregnancy test ^d	X	X	X	X	X
Collect start date (first day) of last menstrual cycle for women having menstrual cycles	X	X	X	X	X
Clinical laboratory determinations ^e	X	X	X	X	X
eDiary instructions and training ^f	X				
Participant eDiary data collection ^{fg}			X		
eDiary data (headache duration, frequency, characteristics and symptoms, acute medication use, AIM-D, Activity Level and Activity Limitation) and compliance review ^h		X	X	X	
MSQ v2.1 (eTablet) ^{i,j}	X	X	X	X	X
C-SSRS (eTablet) ^k	X	X	X	X	X
Collect eDiary					X
Dispense atogepant	X	X	X		
Review atogepant compliance and accountability		X	X	X	
Adverse events				X	
Concomitant medications/concurrent procedures				X	

- a After providing informed consent for this study, Visit 1 will be conducted on the same day as Visit 7/Visit 8 of the lead-in study (Study 3101-303-002 [Phase 3 CM]); procedures conducted as part of Visit 7 of the lead-in study should not be repeated. Visit 1 must be conducted in office. All other visits, should be conducted in office unless it is necessary to conduct a remote visits for the safety of participants (eg, COVID-19 or other pandemic); for details please refer to the Remote Visit Schedule of Assessments in [Attachment 12.3](#)).
- b Medical history will be collected for participants who have a gap between the last visit of the lead-in study and Visit 1 of this extension study and only new medical history during the gap need to be collected.
- c Vital sign measurements: weight, sitting and standing pulse rate, respiratory rate, sitting and standing blood pressure, and body temperature.
- d For WOCBP only, a urine pregnancy test will be performed at all visits.
- e Clinical laboratory determinations include chemistry, hematology, coagulation parameters (INR), and urinalysis to be collected for all visits. Samples for serology and the urine drug screen will be collected only at Visit 1.
- f Participants should begin using the eDiary at Visit 1 and for the duration of the treatment period.
- g Daily eDiary data collection includes: headache frequency, duration, characteristics, symptoms, acute medication use, AIM-D, Activity Level, and Activity Limitation.
- h Participants must bring their eDiary to all visits (except Visit 5).
- i Participant will complete on eTablet.
- j PRO measures should be administered prior to any tests and/or evaluations unless indicated otherwise in the protocol.
- k At all visits, the “Since Last Visit” C-SSRS will be completed for all participants. Clinicians will complete on eTablet.

1 Background and Clinical Rationale

1.1 Background

According to the Guidelines for Prevention and Treatment of Migraine in China (Yu 2016), the prevalence of migraine in China is 9.3%, with a distribution across males and females similar to that of the United States. Migraine affects 18% of women and 6% of men in the United States with peak prevalence occurring between the ages of 25 and 55 years. Approximately one-third of patients with migraines have 3 or more migraine attacks per month, and over half report severe impairment or the need for bed rest (Lipton 2007). In the United States alone, work loss due to migraine is estimated to cost ~ \$13 billion annually (Hu 1999). Prevalence is similar in Europe, with migraine headache affecting on average 17.6% of women and 8% of men (Stovner 2010). Globally, migraine is the 3rd leading cause of years lived with disability with an estimated global prevalence of 14.1% (GBD 2016). Migraine was ranked seventh highest among specific causes of disability globally (Steiner 2013).

Migraine is typically characterized by attacks of throbbing, unilateral headache of moderate or severe pain intensity, associated with nausea, vomiting, and/or sensitivity to light (photophobia) and sound (phonophobia). In about 25% of individuals, the migraine headache is preceded by focal neurological dysfunction (aura). Improving diagnosis and optimizing treatments for migraine have been recognized as critically important to overcoming current barriers to reduce the global burden of migraine.

Because there are no biological markers for migraine, diagnosis is based on clinical history, examination, and the exclusion of other headache disorders. Physicians apply clinical criteria to guide diagnoses and subsequent treatment. Episodic migraine is a syndrome diagnosis applied to patients with migraine (with or without aura) who have 1 to 14 headache days per month. CM is a specific ICHD-3 diagnosis applied to a subset of patients with ≥ 15 headache days per month (Katsarava 2012; Olesen 2004; ICHD-3 2018). This study will evaluate the safety and tolerability of atogepant in participants with CM.

1.2 Overview of Atogepant

Atogepant is a potent, selective, oral CGRP receptor antagonist being developed for migraine prevention. Additional information on non-clinical pharmacology, toxicology, and PK properties of atogepant can be found in the investigator's brochure.

A Phase 2/3 clinical study, CGP-MD-01, compared atogepant 10 mg once daily, atogepant 30 mg once daily, atogepant 30 mg twice a day, atogepant 60 mg once daily, and atogepant 60 mg twice a day to placebo. Overall, all the atogepant doses tested were well tolerated. For the primary efficacy endpoint of change from baseline in mean monthly migraine days across the 12-week treatment period, all atogepant doses demonstrated a statistically significant reduction compared with placebo in patients with episodic migraine.

The ongoing global study 3101-303-002 to evaluate atogepant for the prevention of CM will further explore the dose range that demonstrated statistically significant improvement in the reduction of migraine compared to placebo in Study CGP-MD-01. Study 3101-303-002 will serve as the lead-in study for the current extension study.

1.3 Study Rationale

The purpose of this study is to evaluate the safety and tolerability of atogepant 60 mg once daily, as well as efficacy, when taken for 12 weeks for the prevention of CM.

1.4 Rationale for Doses and Dose Regimens Selected

The Phase 3 pivotal study to evaluate atogepant will test a maximum dose of 60 mg once daily. For this reason, the same dose of 60 mg once daily has been selected to evaluate the safety and tolerability of atogepant for the prevention of CM in this safety extension study.

2 Study Objective and Clinical Hypothesis

2.1 Study Objective

Safety and Tolerability: To evaluate the safety and tolerability of treatment with atogepant 60 mg once daily over a 12-week duration for the prevention of migraine in Chinese participants who completed Study 3101-303-002 (CM).

Efficacy: To evaluate the efficacy of treatment with atogepant 60 mg once daily when administered over 12 weeks for the prevention of migraine in Chinese participants with CM.

2.2 Clinical Hypothesis

Atogepant 60 mg once daily is safe and well tolerated when administered over 12 weeks for the prevention of migraine in Chinese participants with CM who completed lead-in study 3101-303-002.

3 Study Design

3.1 Structure

This is a multicenter, open-label, 12-week, safety extension study conducted in China. Participants will be treated with atogepant 60 mg once daily.

The study will consist of a 12-week treatment period and a 4-week safety follow-up period.

After signing the informed consent, Chinese participants will directly rollover from Study 3101-303-002 (Phase 3 CM); hereafter referred to as the lead-in study. As such, participants will have Visit 7 from the lead-in study function as Visit 1 for this extension study. After Visit 1, study visits will occur every 4 weeks during the 12-week treatment period. A safety follow-up visit will occur 4 weeks after the last dose of atogepant.

Note, there may be participants who complete Visit 7 in the lead-in study before this extension study (3101-311-002) has been initiated. Those participants should complete Visit 7/ET and Visit 8/EOS Visit (including discontinuation of study intervention) per the lead-in study Schedule of Visits and Procedures.

Depending on the timing of the initiation of this extension study (3101-311-002) in relation to each participant's planned Visit 8 schedule in the lead-in study, Visit 1 for this extension study can be conducted on the same day as Visit 8/EOS Visit for the lead-in study, or soon thereafter.

- If this extension study is initiated prior to the participant's planned Visit 8 in the lead-in study, then Visit 8/EOS Visit in the lead-in study should be conducted on the same day as Visit 1 for this extension study (3101-311-002).
- If this extension study is not initiated prior to the participant's planned Visit 8 in the lead-in study (ie, there is a gap between Visit 8 of the lead-in study and Visit 1 of this extension study), then Visit 8/EOS Visit should be conducted as planned per the lead-in study Schedule of Visits and Procedures. When this extension study is initiated, the participant should return to the clinic as soon as possible, and Visit 1 should be conducted per [Table 1](#) Schedule of Visits and Procedures.

Participants will return to the clinic for safety assessments at 4, 8, and 12 weeks relative to Visit 1 (Day 1). A safety follow-up visit will occur 4 weeks after the last dose of atogepant 60 mg once daily. For details, please see [Table 1](#) Schedule of Visits and Procedures.

The primary objective of the study is to assess the safety and tolerability of treatment with atogepant 60 mg once daily over a 12-week duration for the prevention of migraine in Chinese participants who completed Study 3101-303-002. The planned safety assessments include collection of AEs, clinical laboratory determinations, ECGs, vital sign measurements, physical examinations, and the C-SSRS.

3.2 Data Safety Monitoring Board

Not applicable

3.3 Adjudication Committee

An Adjudication Charter will be established and will describe the process for the surveillance, monitoring, and adjudication by an external Clinical Adjudication Committee of events of post-treatment elevations of ALT and/or AST $\geq 3 \times$ ULN. The purpose of this charter will be to provide a standardized process for the adjudication of the events in order to determine whether the elevation was related to atogepant.

4 Study Population and Entry Criteria

4.1 Number of Participants

All participants who complete Study 3101-303-002, and meet all eligibility requirements, may participate in this study. Approximately 120 participants will be enrolled at approximately 25 centers in China.

4.2 Study Population Characteristics

Participants eligible to participate in this study completed Visit 7, and Visit 8 if applicable, of Study 3101-303-002 without significant protocol deviations (eg, noncompliance to protocol-required procedures), meet the inclusion criteria, and do not meet the exclusion criteria for this study.

4.3 Inclusion Criteria

1. Written informed consent and participant privacy information (eg, written authorization for use and release of health and research study information) obtained from the participant prior to initiation of any study-specific procedures.
2. Eligible participants who completed the double-blind treatment period (Visit 7) and the follow-up period (Visit 8), if applicable, depending on the timing of study initiation, of Study 3101-303-002 without significant protocol deviations (eg, noncompliance to protocol-required procedures) and who did not experience an AE that, in the investigator's opinion, may indicate an unacceptable safety risk.
3. Participants must be using a medically acceptable and effective method of birth control during the course of the entire study, as defined in Section 4.5.3.

4.4 Exclusion Criteria

1. Requirement for any medication, diet (ie, grapefruit juice), or nonpharmacological treatment that is on the list of prohibited concomitant medications or treatments (see Section 4.5.2 and [Attachment 12.2](#)) that cannot be discontinued or switched to an allowable alternative medication or treatment. Participants from lead-in study 3101-303-002 taking 1 medication with demonstrated efficacy for the prevention of migraine may participate in the current study provided that the dose was stable for at least 12 weeks prior to Visit 1 of the lead-in study and the participant is willing and able to maintain taking this medication at a stable dose and dosage regimen throughout the study.
2. Female participant is pregnant, planning to become pregnant during the course of the study, or currently lactating. Women of childbearing potential must have a negative urine pregnancy test at Visit 1.
3. An ECG with clinically significant abnormalities at Visit 1 as determined by the investigator.
4. Hypertension as defined by sitting systolic BP > 160 mm Hg or sitting diastolic BP > 100 mm Hg at Visit 1. Vital sign measurements that exceed these limits may be repeated only once.
5. Significant risk of self-harm based on clinical interview and responses on the C-SSRS, or of harm to others in the opinion of the investigator; participants must be excluded if they report suicidal ideation with intent, with or without a plan, (ie, Type 4 or 5 on the C-SSRS) since the last visit.

6. Any clinically significant hematologic, endocrine, cardiovascular, pulmonary, renal, hepatic, GI, or neurologic disease.
7. Participant has a condition or is in a situation which in the investigator's opinion may put the participant at significant risk, may confound the study results, or may interfere significantly with participation in the study.
8. Any medical or other reasons (eg, unlikely to adhere to the study procedures, keep appointments, or is planning to relocate during the study) that, in the investigator's opinion, might indicate that the participant is unsuitable for participation in the study.

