6.1.7 Columbia-Suicide Severity Rating Scale (C-SSRS)

The C-SSRS is a clinician-rated instrument that reports the severity of both suicidal ideation and behavior. Suicidal ideation is classified on a 5-item scale: 1 (wish to be dead), 2 (nonspecific active suicidal thoughts), 3 (active suicidal ideation with any methods [not plan] without intent to act), 4 (active suicidal ideation with some intent to act, without specific plan), and 5 (active suicidal ideation with specific plan and intent). The C-SSRS also captures information about the intensity of ideation, specifically the frequency, duration, controllability, deterrents, and reasons for the most severe types of ideation. Suicidal behavior is classified on a 5-item scale: 0 (no suicidal behavior), 1 (preparatory acts or behavior), 2 (aborted attempt), 3 (interrupted attempt),

and 4 (actual attempt). More than 1 classification can be selected provided they represent separate episodes. For actual attempts only, the actual or potential lethality is classified for the initial, most lethal, and most recent attempts. The C-SSRS will be completed at all study visits. At all visits the C-SSRS will be completed for ideation and behavior since last visit for all participants. The C-SSRS will be completed on the eTablet by the investigator or designee with current and valid training in administering the assessment. A participant should not be released from the study center until the results of C-SSRS are reviewed and it is confirmed that the participant is not considered to be at risk. Participants who reply with “yes” to questions 4 or 5 in the suicidal ideation section or “yes” to any question in the suicidal behavior section of the C-SSRS at Visits 2 through 3 must be withdrawn from the study and should receive appropriate follow-up as in routine clinical practice, including the ET (Visit 4) and the safety follow-up (Visit 5) assessments.

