8.9 Withdrawal Criteria

- **Participants with the following at Visit 1:**
 - **Laboratory Results:**
 - ALT or AST > 1 x ULN OR
 - total bilirubin > 1 x ULN (except for participants with a diagnosis of Gilbert's disease) OR
 - serum albumin < 2.8 g/dL
 - Positive result on the urine drug screen unless explained by concomitant medication use (eg, opioids prescribed for migraine pain).
 - Positive result on anti-hepatitis A IgM antibody, hepatitis B surface antigen, anti-hepatitis C antibody testing, or anti-hepatitis E IgM antibody.
 - **ECG Results:**
 - QTcF > 450 msec for males and QTcF > 470 msec for females on the final central vendor ECG report
 - Clinically significant cardiac rhythm or conduction abnormalities (eg, atrial fibrillation, second- or third-degree heart block)
- **Participants with the following at any study visit:**
 - Female participants who become pregnant (Section 9.4)
 - Participants who meet atogepant discontinuation criteria related to abnormal liver function tests (Section 9.5), and advised not to be rechallenged, will be withdrawn from the study and should refrain from taking atogepant.
 - Participants who reply with “yes” to questions 4 or 5 in the suicidal ideation section or “yes” to any question in the suicidal behavior section of the C-SSRS at Visits 2 and 3 must be withdrawn from the study.
 - A participant with a condition and/or a situation that, in the investigator's opinion, may put the participant at significant risk, may confound the study results, or may interfere significantly with the participant's participation in the study may be withdrawn from treatment.

All withdrawn participants should receive appropriate follow-up as in routine clinical practice, including the Visit 4 (ET) and Visit 5 (safety follow-up/EOS) assessments.

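### Suicidal behaviour on the C-SSRS forces withdrawal at Visits 2 and 3 but is not an automatic exclusion at Visit 1, where dosing starts

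*Protocol*

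**What the plan says.** Protocol 4.4, criterion 5, has two parts. The opening part is a risk judgement: "Significant risk of self-harm based on clinical interview and responses on the C-SSRS", or a risk of harm to others in the investigator's opinion. The second part is a fixed rule: "participants must be excluded if they report suicidal ideation with intent, with or without a plan, (ie, Type 4 or 5 on the C-SSRS", counted since the last visit. The Key Exclusion Criteria in the Protocol Summary repeat the fixed rule with the same scope: "ie, Type 4 or 5 on the C-SSRS) since the last visit, must be excluded".

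On treatment the trigger is wider. Besides a positive answer to ideation questions 4 or 5, Protocol 6.1.7 covers a positive answer "to any question in the suicidal behavior section of the C-SSRS at Visits 2 through 3 must be withdrawn from the study". Protocol 8.9 repeats this: "to any question in the suicidal behavior section of the C-SSRS at Visits 2 and 3 must be withdrawn from the study".

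Protocol 6.1.2 also puts Type 4 or 5 ideation and any suicidal behaviour together as one adverse event of special interest. Under 6.1.7 the Since Last Visit form, with both its ideation and behaviour sections, is completed at every visit, Visit 1 included.

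**The concern.** The protocol treats behaviour as equal to Type 4 or 5 ideation in its special-interest definition and in both on-treatment withdrawal rules. The entry rule is the exception. Read literally, ideation with some intent to act bars entry automatically, while a preparatory act, or an aborted, interrupted or actual attempt, does not.

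Visit 1 is where open-label dosing begins, and a site could reasonably infer that behaviour was left to its discretion because only ideation is named. What is at stake is participant safety and consistent handling. The data are not lost: the answer is recorded on the Visit 1 form, and SAP 5.4.4.4 lists participants in the Safety population who have suicidal ideation or behaviour on the C-SSRS.

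**Working it through.** The plan gives no figure to reproduce. The check compares the rules, followed by a rough calculation of how often the gap could matter.

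**Automatic triggers at each visit where atogepant is dispensed (Protocol Table 1)**

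| Visit | Ideation 4 or 5 | Any suicidal behaviour | Source |
|---|---|---|---|
| 1 | Must be excluded | No automatic rule | 4.4 criterion 5; Protocol Summary |
| 2 | Must be withdrawn | Must be withdrawn | 6.1.7; 8.9 |
| 3 | Must be withdrawn | Must be withdrawn | 6.1.7; 8.9 |

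The behaviour rule operates at 2 of the 3 dispensing visits.

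**Does another section supply the missing rule at Visit 1?**

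- Protocol 8.9 has a block headed "Participants with the following at Visit 1". It contains laboratory, drug-screen, serology and ECG results and no C-SSRS item.
- The C-SSRS item in 8.9 stands under the heading for any study visit, but its own wording limits it to Visits 2 and 3.
- Protocol 8.4.1.1 makes the remaining Visit 1 procedures conditional on the entry criteria and mentions ECG, pregnancy test and vital signs as examples. For the C-SSRS this leads back to criterion 5.
- The other routes depend on judgement: the opening part of criterion 5; criteria 7 and 8; inclusion criterion 2 (no prior event that "may indicate an unacceptable safety risk" in the investigator's opinion); the significant-risk clause of 8.9; and the check in 6.1.7 that, before release, "it is confirmed that the participant is not considered to be at risk".

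**Would the later rule catch the event?** No. The form covers the interval since the last visit, so behaviour reported at Visit 1 falls before the Visit 2 interval. A participant enrolled despite that report would not be withdrawn at Visit 2 because of it.

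**Would lead-in rules catch it?** They might for direct rollovers, but the lead-in protocol is not among the documents. Protocol 3.1 and 8.3 also allow a gap between lead-in Visit 8 and extension Visit 1, with no stated maximum. A lead-in visit rule cannot act on behaviour that occurs in that gap.

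**Frequency.** Let p be the chance that a participant reports suicidal behaviour at Visit 1 without Type 4 or 5 ideation. The documents give no value, so p = 0.001 to 0.01 is an assumed range. The number of participants n is about 3 (SAP 3) or about 120 (Protocol 4.1 and 7.5). The chance of at least one such report is 1 − (1 − p)^n:

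- n = 3: 1 − 0.999^3 = 0.0030; 1 − 0.99^3 = 0.0297
- n = 120: 1 − 0.999^120 = 0.1131; 1 − 0.99^120 = 0.7006

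These are chances that the answer occurs. The chance that such a participant is then dosed is lower, because the judgement clauses would stop some or most of them.

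**The case against.** The best counter-argument is that criterion 5 already does the work. Its opening part is an exclusion in its own right and draws on C-SSRS responses, which include the behaviour answers; the Protocol Summary likewise ties self-harm risk to the C-SSRS and reserves investigator opinion for harm to others. For harm to follow, an investigator would have to read a recorded attempt or preparatory act, find no significant risk, and dispense. The comparison with Visits 2 and 3 is also imperfect: on treatment the general risk clause in 8.9 only permits withdrawal, so a fixed rule adds more there than at entry, where meeting the risk clause already bars the participant. Finally, with about 3 participants at about 2 centres (SAP 1.2 and 3), variation between sites is a small matter.

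Much of this stands. A participant reporting behaviour would probably be excluded in practice, and at the current size the issue is unlikely to arise. But the opening part has no threshold. The sponsor added a fixed rule for Type 4 or 5 ideation even though the same opening part was there, and removed discretion over behaviour at Visits 2 and 3. No section gives a reason for treating behaviour differently at entry.

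**Conclusion.** The concern holds. At Visit 1 suicidal behaviour is excluded by judgement and not by rule, although the same answer requires withdrawal at the next two visits. What is missing is an explicit rule; protection as such is not absent. At the SAP's expected 3 participants, the chance that the situation arises at all is 0.3% to 3.0% under the assumed rate; the 11% to 70% range applies only to the protocol's 120, a size the SAP no longer expects. No estimate, listing or conclusion changes. This is a recommended safety harmonisation and not an essential correction. The comparison of rules rests on the text alone; the frequencies rest on the assumed rate. Whether the lead-in study's own rules would also act on direct rollovers cannot be settled from these documents.

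**What to change.** Extend the mandatory clause of criterion 5 in Protocol 4.4, and its copy in the Protocol Summary, so that exclusion follows from ideation Type 4 or 5 or any suicidal behaviour since the last visit. This is the trigger already used at Visits 2 and 3.

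The text change is one clause in two places and needs no new data, since the behaviour section is already completed at Visit 1. A rare participant would become ineligible by rule instead of by judgement. Because an entry criterion changes, Protocol 10.3 calls for an amendment with prior IRB/IEC approval. The SAP's summary of changes says that enrolment of Chinese patients in the lead-in study has stopped, so few further entrants may benefit; the wording is still worth correcting if this protocol serves as a model for a larger study.
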